13.1. Overall

“Table 1.1 Contract with institutions and number of patients”

Analysis objects: Number of contract institutions, number of patients included in the safety analysis set, mean number of patients per institution, maximum number of patients per institution, minimum number of patients per institution

Purpose of analysis: To confirm the contract and the number of patients of the institutions.

Note: The number of contract institutions, mean number of patients per institution, maximum number of patients per institution, and minimum number of patients per institution with the patients included in the safety analysis set should be analyzed.

“Table 1.2 Patient disposition diagram”

Analysis items: Number of patients enrolled, number of patients with returned CRFs, number of patients without returned CRFs, number of patients with uncorrectable CRFs, number of patients with fixed CRFs, number of patients with unfixed CRFs, number of patients included in the safety analysis set, number of patients excluded from the safety analysis set (and by reason), number of patients included in the efficacy analysis set, number of patients excluded from the efficacy analysis set (and by reason).

Purpose of analysis: To confirm the disposition of the analysis sets.

Note: The numbers of patients should be shown in a flow chart.
The items with no reason for exclusion should not be read out for each item.

“Table 1.2 (Appendix) Patient composition diagram”

Analysis object: Number of patients included in the efficacy analysis set

Purpose of analysis: To confirm the number of patients evaluated and the number of unevaluable patients per efficacy endpoint.

Note: The numbers of patients should be shown in a flow chart.

“Table 1.2 Patient disposition diagram (third CRF)”

Analysis object: Patients included in the efficacy analysis set (third CRF)

Purpose of analysis: To confirm the disposition of the number of patients per efficacy endpoint evaluable in the third CRF when allocating the patients included in the efficacy analysis set in the third CRF into the following four groups: the “treatment continuing” group, “treatment discontinued” group, “survey discontinued” group or “other” group.

Note: None in particular.

“Table 1.3.1 Progress of the CRF”

Analysis object: Patients included in the safety analysis set

Purpose of analysis: To indicate the number of overall patients with fixed CRFs and by CRF for the patients included in the safety analysis set and efficacy analysis set.

Note: None in particular.

“Table 1.3.2 List of patients”

Analysis object: Patients with fixed CRFs

Purpose of analysis: To confirm the details of the overall patients.

Note: To indicate the details in a list.

“Table 1.3.3 Lists of patients excluded from safety analysis set and patients excluded from efficacy analysis set (including reasons for exclusion)”

Analysis object: Patients excluded from the safety analysis set, patients excluded from the efficacy analysis set

Purpose of analysis: To confirm the reasons for excluding from the safety analysis set and efficacy analysis set.

Note: To indicate the case numbers and reasons for exclusion in a list.

<Detailed note>

*Where one patient has more than one reason for exclusion, they should be linked with “commas” for output.

“Table 1.4 Disposition by Hospital of the University of Occupational and Environmental Health, Japan”

Analysis object: Patients included in the safety analysis set, patients included in the efficacy analysis set (DAS28-4CRP)

Purpose of analysis: To indicate the incidence of ADRs and the results of χ^2 tests in the patients included in the safety analysis set and the response rate in EULAR DAS28-4CRP and the results of χ^2 tests in EULAR DAS28-4CRP at the final evaluation in patients included in the efficacy analysis set (DAS28-4CRP) per institution analyzed (other than Hospital of the University of Occupational and Environmental Health, Japan and University of

Occupational and Environmental Health, Japan).

Note: Good Response and Moderate Response should be judged as “effective” for the EULAR DAS28-4CRP response at the final evaluation.

“Table 1.5 Disposition by mode of Humira administration”

Analysis object: Patients included in the safety analysis set, patients included in the efficacy analysis set (DAS28-4CRP)

Purpose of analysis: To indicate the incidence of ADRs and the results of χ^2 tests in the patients included in the safety analysis set and the response rate in EULAR DAS28-4CRP and the results of χ^2 tests at the final evaluation in patients included in the efficacy analysis set (DAS28-4CRP).

The category for mode of administration should follow “11. Data-layer separation.”

Note: Good Response and Moderate Response should be judged as “effective” for the EULAR DAS28-4CRP response at the final evaluation.

13.2. Safety

“Table 2.1 Distribution status by patient background factor”

Analysis object: Patients included in the safety analysis set

Purpose of analysis: To calculate the number and percentage of patients by patient background factor at the start of treatment, or summary statistics by work status.

The patient background factors should follow “11. Data-layer separation.”

Note: Complication: liver disorder (hepatitis) ... the denominator of the percentage should be the number of patients with “hepatitis.”

Complication: liver disorder (hepatitis virus carrier) ... the denominator of the percentage should be the number of “hepatitis virus carriers.”

History of allergy (details) ... the denominator of the percentage should be the number of patients “with” a history of allergy.

Smoking history (details) ... the denominator of the percentage should be the number of patients “with” a smoking history.

Smoking history: smoking years (previously) ... the denominator of the percentage should be the duration of smoking (year) of the patient “previously smoking.”

Smoking history: smoking years (currently) ... the denominator of the percentage should be the duration of smoking (year) of the patient “currently smoking.”

Concomitant drug ... the data at the start of Humira treatment and duration of Humira treatment should be analyzed, respectively.

<Detailed note>

- 1) The denominator of the percentage should be the number of patients with “hepatitis.”
- 2) The denominator of the percentage should be the number of “hepatitis virus carriers.”

- 3) The denominator of the percentage should be the number of patients “with” a history of allergy.
- 4) The denominator of the percentage should be the number of patients “with” a smoking history.
- 5) The data on the duration of smoking (year) of the patients “previously smoking” should be analyzed.
- 6) The data on the duration of smoking (year) of the patients “currently smoking” should be analyzed.
- 7) The data at the start of Humira treatment should be analyzed.
- 8) The data during the Humira treatment should be analyzed.

“Table 3.1 Humira treatment status”

Analysis object: Patients included in the safety analysis set

Purpose of analysis: To calculate the number and percentage of patients or summary statistics by mode of administration and period to treatment completion concerning Humira treatment status.
The category for mode of administration should follow “11. Data-layer separation.”

Note: 10.1 “Humira treatment period” should be used as the total treatment period including washout as the period to treatment completion.
<Detailed note>

- 1) When the patient was continuing the treatment at week 104, the patient was tabulated as “continuing treatment.”

“Table 3.2.1 Disposition of reasons for discontinuation of Humira treatment (first and second CRFs)”

Analysis object: Patients included in the safety analysis set

Purpose of analysis: To indicate the number and percentage of patients for the disposition of the reasons for discontinuation of Humira treatment.
The reasons for discontinuation should follow “11. Data-layer separation.”

Note: The denominator of the percentage of the number of discontinued patients should be the number of patients included in the safety analysis set, and the denominator of the percentage of the number of patients by reason for discontinuation should be the number of overall discontinued patients.
<Detailed note>

When a patient is applicable to more than one items, each of them was counted.

“Table 3.2.2 Disposition of reasons for survey discontinuation (third CRF)”

Analysis object: Patients included in the safety analysis set

Purpose of analysis: To indicate the number and percentage of patients for the disposition of the reasons for discontinuation of the survey discontinued patients in the third CRF. The number and percentage of patients should also be indicated for the

disposition of the reasons for discontinuation of the patient who discontinued treatment in the third CRF. The reasons for discontinuation should follow “11. Data-layer separation.”

Note: The denominator of the percentage of the number of discontinued patients should be the number of patients with fixed CRFs at week 104 among the patients included in the safety analysis set, and the denominator of the percentage of the number of patients by reason for discontinuation should be the number of overall discontinued patients by reason for survey discontinuation and treatment discontinuation.

The patients applicable to survey discontinuation should not be included in the number of treatment discontinued patients. The reasons for treatment discontinuation should be the change in dose/number of doses or reason for discontinuation of the final record in the “Humira treatment status” in the third CRF.

<Detailed note>

When a patient is applicable to more than one items, each of them was counted.

“Table 5.1 Frequency of ADRs by seriousness”

Analysis object: Patients included in the safety analysis set

Purpose of analysis: To indicate the number of patients analyzed, number of patients who developed all events, number and percentage of ADRs, number and percentage of SOC and PT by seriousness regarding ADRs. The same PT of the same patient should be summarized collectively, and in that sense, the most serious event should be tabulated.

Note: The information on novelty should not be granted.

The next forms should be prepared in the same manner.

“Table 5.1.1 Frequency of AEs by seriousness”

Analysis object: Patients included in the safety analysis set

“Table 5.1.2 Frequency of ADRs by seriousness (excluded patients)”

Analysis object: Patients excluded from the safety analysis set

Note: Among the patients with fixed CRFs, the patients excluded from the safety analysis set should be tabulated.

“Table 5.1.3 Frequency of ADRs by seriousness (Hospital of the University of Occupational and Environmental Health, Japan)”

Analysis object: Patients included in the safety analysis set

Note: patients treated at the Hospital of the University of Occupational and Environmental Health, Japan should be tabulated.

“Table 5.1.4 Frequency of ADRs by seriousness (other than Hospital of the University of Occupational and Environmental Health, Japan)”

Analysis object: Patients included in the safety analysis set

Note: Patients excluded from those treated at the Hospital of the University of Occupational and Environmental Health, Japan should be tabulated.

“Table 5.2.1 Frequency of ADRs by time of onset”

Analysis object: Patients included in the safety analysis set

Purpose of analysis: To indicate the number of patients analyzed, number of patients who developed all ADRs, number and percentage of ADRs, number and percentage of SOC and PT by time of onset regarding ADRs.

Note: The information on novelty should not be granted.

Categories for time of onset of ADRs: “start of treatment to week 24,” “week 24 to week 52,” “week 52 to week 108,” and “after completion of treatment.”

“Table 5.2.2 Frequency of serious ADRs by time of onset”

Analysis object: Patients included in the safety analysis set

Purpose of analysis: To indicate the number of patients analyzed, number of patients who developed all events, number and percentage of ADRs, number and percentage of SOC and PT by time of onset regarding serious ADRs.

Note: The information on novelty should not be granted.

“5.2.3 Summary of serious adverse drug reactions by each MTX Dose of Baseline”

Analysis object: Patients included in the safety analysis set

Purpose of analysis: To indicate the number of patients analyzed, number of patients who developed ADRs, number and percentage of ADRs, number and percentage of SOC and PT by category of MTX dose at the start of treatment regarding serious ADRs.

Note: Category of MTX dose at the start of treatment

“Baseline MTX 12<= $<$ 14.0,” “Baseline MTX 14.0<= $<$ 16.0,” “Baseline MTX 16.0<=”

This should be prepared only at the time of literature analysis.

“Table 5.2.4 Summary of serious adverse drug reactions by each MTX Dose of Baseline (Event/100 Patient Years)”

Analysis object: Patients included in the safety analysis set

Purpose of analysis: To indicate the number of patients analyzed, number of patients who developed ADRs, number and percentage of ADRs (unit: 100 persons/year), number and percentage of SOC and PT by category of MTX dose at the start of treatment regarding serious ADRs during Humira treatment.

Note: Category of MTX dose at the start of treatment

“Baseline MTX 12<= $<$ 14.0,” “Baseline MTX 14.0<= $<$ 16.0,” “Baseline MTX 16.0<=”

Percentage of patients who develop ADRs (person/year) = “number of serious ADRs / total follow-up period)

This should be prepared only at the time of literature analysis.

“Table 5.3.1 List of AEs occurred during treatment and after completion of treatment”

Analysis object: Patients included in the safety analysis set

Purpose of analysis: To indicate the number of overall ADRs, SOC and PT occurred by case status (overall, patients who are continuing Humira treatment, patients who discontinued Humira treatment) regarding AEs.

The patients who discontinued Humira treatment should be indicated by timing of treatment (during treatment, after treatment).

Note: The definitions of case status should be as follows.

- During treatment

Events that occurred between the date of initial Humira treatment and the date of final Humira treatment.

- After treatment

Events that occurred after the date of final Humira treatment.

“Table 5.3.2 List of serious AEs occurred during treatment and after completion of treatment”

Analysis object: Patients included in the safety analysis set

Purpose of analysis: To indicate the number of overall AEs, SOC and PT occurred by case status (overall, patients who are continuing Humira treatment, patients who discontinued Humira treatment) per timing of treatment (during treatment, after completion of treatment) regarding serious AEs.

Note: The definitions of the patients who are continuing Humira treatment and the patients who discontinued Humira treatment should be same as “Table 5.3.1 List of AEs occurred during treatment and after completion of treatment.”

“Table 5.4 Incidence of ADRs by patient background factor”

Analysis object: Patients included in the safety analysis set

Purpose of analysis: To indicate the overall ADRs, and the number and percentage the patients who developed ADRs by seriousness by patient background factor. The categories of patient background factors should follow “11. Data-layer separation,” and when ADRs of the same PT occurred in the same patient, and the number of the ADR should be rounded to a severe event before tabulation.

<Detailed note>

- 1) The data at the start of Humira treatment should be analyzed.

- 2) The data during the Humira treatment should be analyzed.

“Table 5.4.1 Incidence of ADRs by patient background factor (Hospital for the University of Occupational and Environmental Health, Japan)”

Analysis object: patients included in the safety analysis set

Note: Patients treated at the Hospital of the University of Occupational and Environmental Health, Japan should be tabulated.

“Table 5.4.2 Incidence of ADRs by patient background factor (other than Hospital for the University of Occupational and Environmental Health, Japan)”

Analysis object: patients included in the safety analysis set

Note: Patients excluded from those treated at the Hospital of the University of Occupational and Environmental Health, Japan should be tabulated.

“Table 5.5.1.1 Frequency of ADRs by seriousness with or without liver disorder”

Analysis object: Patients included in the safety analysis set

Purpose of analysis: To indicate the number of patients analyzed, number of patients who developed ADRs, number and percentage of ADRs, number and percentage of SOC and PT by seriousness with or without liver disorder regarding ADRs. Additionally, the stratified items with a significant difference in Table 5.4 should also be tabulated.

Note: The information on novelty should not be granted. This should be prepared only when there are more than ten patients or 3% of the patients are applicable to the category of interest.

The next forms should be prepared in the same manner.

“Table 5.5.1.2 Frequency of ADRs by seriousness with or without renal disorder”

Note: The categories of the tabulation should be with or without renal disorder.

“Table 5.5.1.3 Frequency of ADRs by seriousness in elderly or non-elderly”

Note: The categories of the tabulation should be by elderly or non-elderly.

“Table 5.5.1.4 Frequency of ADRs by seriousness by mode of Humira administration”

Note: The categories of the tabulation should follow the mode of Humira administration in Table 3.1.

“Table 5.5.2.1 Frequency of ADRs by outcome with or without liver disorder”

Analysis object: Patients included in the safety analysis set

Purpose of analysis: to indicate the number of patients analyzed, number of patients who developed all ADRs, number and percentage of ADRs, number and percentage of SOC and PT with or without liver disorder by outcome regarding ADRs.

Note: The information on novelty should not be granted.

This should be prepared only when there are more than ten patients or 3% of the patients are applicable to the category of interest.

The next forms should be prepared in the same manner.

“Table 5.5.2.2 Frequency of ADRs by outcome with or without renal disorder”

Note: The categories of the tabulation should be with or without renal disorder.

“Table 5.5.2.3 Frequency of ADRs by outcome by elderly or non-elderly”

Note: The categories of the tabulation should be by elderly or non-elderly.

“Table 5.5.2.4 Frequency of ADRs by outcome by mode of Humira administration”

Note: The categories of the tabulation should follow the mode of Humira administration in Table 3.1.

“Table 5.6 Appended Form 2”

Analysis object: Patients included in the safety analysis set

Purpose of analysis: To prepare for reexamination.

Note: None in particular.

“Table 5.7 Appended Form 3”

Analysis object: Patients with fixed CRFs

Purpose of analysis: To indicate a list of summaries of the patients surveyed.

Note: A specification should be prepared separately for the details of analysis specification.

“Table 5.8.1 The Number of Weeks to Discontinuation”

Analysis object: Patients included in the safety analysis set

Purpose of analysis: To illustrate the survival curve of the rate of Humira continuation up to week 104. The survival curve should be illustrated by means of the SAS LIFETEST procedure.

Note: This form should be prepared only at the time of literature analysis.

“Table 5.8.2 The Number of Weeks to Discontinuation”

Analysis object: Patients included in the safety analysis set

Purpose of analysis: To illustrate the survival curve of the rate of Humira continuation up to week 104. The survival curve should be illustrated by using the SAS LIFETEST procedure, and the patients who are continuously receiving Humira even after Day 728 should be handled as the censored cases.

Note: This form should be prepared only at the time of literature analysis.

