7.5 Study Duration

- 1) The duration of the whole PMOS is estimated to be about 4 years.

- Study start: September 2012
-

- Recruiting phase: September 2012 - December 2014
 - Data completion: January 2018
 - End of study: The date on which statistical analysis dataset for Clinical Study Report becomes available
 - Data analysis and final report: April 2018 – October 2018
- 2) For each individual patient, the PMOS starts with the enrollment at the beginning of the treatment with adalimumab.
- Observation period
 - 104 weeks (or discontinuation of this study)
 - Discontinuation of this study
 - Patients within 52 weeks into this study: When adalimumab treatment is discontinued.
 - Patients after 52 weeks into this study: When any biologics other than adalimumab is administered.

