Reason for discontinuation (third CRF)	Occurrence of AEs, symptom improved, inadequate response, patient refused treatment with Humira, others (pregnancy/desire for pregnancy, others), undescribed
Reason for survey discontinuation	Administration of biological products other than Humira, failed to visit hospital, others, undescribed

<Efficacy endpoints>

Data	Layer separation	
DAS28-4ESR	High Moderate Low Remission	> 5.1 > 3.2 and ≤ 5.1 ≥ 2.6 and ≤ 3.2 < 2.6
DAS28-4CRP	High Moderate Low Remission	> 5.1 > 3.2 and ≤ 5.1 ≥ 2.6 and ≤ 3.2 < 2.6
CDAI	High Moderate Low Remission	> 22.0 > 10.0 and ≤ 22.0 > 2.8 and ≤ 10.0 ≤ 2.8
SDAI	High Moderate Low Remission	> 26.0 > 11.0 and ≤ 26.0 > 3.3 and ≤ 11.0 ≤ 3.3
HAQ-DI	High Moderate Low Remission	> 1.5 > 1.0 and ≤ 1.5 > 0.5 and ≤ 1.0 ≥ 0 and ≤ 0.5
mTSS	Change (≤ 0) Change (≤ 0.5) Change (≤ 1.0)	Change ≤ 0 Change ≤ 0.5 Change ≤ 1.0
Bone erosion score	Change (≤ 0) Change (≤ 0.5) Change (≤ 1.0)	Change ≤ 0 Change ≤ 0.5 Change ≤ 1.0
Joint space narrowing score	Change (≤ 0) Change (≤ 0.5) Change (≤ 1.0)	Change ≤ 0 Change ≤ 0.5 Change ≤ 1.0

*Hereafter, “complete remission” refers to “Remission” in the above table.

12. Handling of data on test/evaluation time

For data entered at each timing of efficacy evaluation excluding mTSS, bone erosion score and joint space narrowing score, the acceptability of data by timing should be judged based on the acceptable range of the timing. The acceptable range of the timing is shown in the table below.

If there is more than one data within the acceptable range of the timing, the data on the closest date to the reference date should be adopted. If there is more than one data within the acceptable range of the timing with the equal number of days from the reference before and after the reference date respectively, the data before the reference date should be adopted.

When evaluating efficacy regarding administration of Humira, it should follow the following provision for the data included in the following acceptable range.

- The data up to the date of final Humira treatment + 28 days should be tabulated.

However, the date of final Humira treatment +28 days is later than the date of survey discontinuation, the data up to the date of survey discontinuation should be tabulated.

This date is called [final evaluation date] in the following.

Timing and period category	Handling of data

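### SAP Table 3.2.2 leaves survey-discontinued patients out of the third-CRF treatment-discontinuation count, so adverse-event and inadequate-response stops by patients who then switch biologic are not tabulated

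*SAP*

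**What the plan says.** Table 3.2.2 (SAP 13.2) covers the third CRF. It gives the "disposition of the reasons for discontinuation of the survey discontinued patients in the third CRF" and, in the same table, the reasons of patients who stopped Humira. A patient is not to appear in both: "The patients applicable to survey discontinuation should not be included in the number of treatment discontinued patients". The stop reason comes from the final entry under Humira treatment status in the third CRF.

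The two reason lists are in SAP section 11:
- Stopping Humira (third CRF): "Occurrence of AEs, symptom improved, inadequate response, patient refused treatment with Humira, others (pregnancy/desire for pregnancy, others), undescribed".
- Survey discontinuation: "Administration of biological products other than Humira, failed to visit hospital, others, undescribed".

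The percentage discontinued has as its denominator what "should be the number of patients with fixed CRFs at week 104 among the patients included in the safety analysis set". The denominator for each reason "should be the number of overall discontinued patients by reason for survey discontinuation and treatment discontinuation".

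Protocol 7.5 ends the study as follows: "Patients after 52 weeks into this study: When any biologics other than adalimumab is administered". Up to week 52 the study ends when adalimumab itself is stopped.

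SAP 10.1 classes a patient whose last fixed CRF is the third as having discontinued Humira if the final treatment record carries a completion date. It makes no exception for patients whose survey also ended.

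**The concern.** Starting another biologic is the protocol's trigger for leaving the study after week 52. A patient who gave up adalimumab for an adverse event or lack of response and then switched meets that trigger, and Table 3.2.2 then drops the patient from the Humira-discontinuation tally. The parallel tally cannot recover the reason, because its list says what happened next (another biologic, missed visits) and not why Humira was stopped.

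At stake is the only specified tabulation of why patients stopped in the second year. Table 3.2.1 covers the first and second CRFs only and has no such exclusion, so a first-year switcher is tabulated by stop reason and a second-year switcher is not. The two periods cannot be compared directly. The number of discontinuers in Table 3.2.2 can also fall below the number implied by 10.1, which Table 5.3.1 uses when it splits adverse events by continuing and discontinued patients.

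**Working it through.** The plan states no figure on this point, so there is nothing to reproduce. The check is a reading of the rules, followed by algebra.

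**Tracing one patient.** Suppose a patient stops Humira in week 70 for inadequate response and starts another biologic in week 74.
1. SAP 10.1: the final record has a completion date, so the patient is a Humira discontinuer.
2. Protocol 7.5: the other biologic ends the study for this patient.
3. Table 3.2.2: as a survey discontinuation, the patient is removed from the treatment-discontinuation tally.
4. Section 11: the only fitting survey reason is the other biologic. Inadequate response is not on that list.

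SAP 10.1 also has a rule for a biologic that starts on the day Humira ends in the third CRF, so the plan expects switchers to have a Humira completion date.

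**Effect on counts.** Let T be the patients kept as treatment-discontinued and S the survey-discontinued patients who stopped Humira. If a of the S stopped for a given reason, the table's count for that reason is short by a, whichever denominator is used.

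**Effect on the improvement share.** Let x of the T, and a fraction r of the S, have stopped for improvement.
- All stoppers: (x + rS)/(T + S).
- Table, separate denominators: x/T. This exceeds the all-stopper share only if r < x/T.
- Table, pooled denominator: x/(T + S). This can never exceed the all-stopper share.

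The wording of the by-reason denominator allows either reading.

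**Range of r (assumed T = 30, x = 10; separate denominators show 33.3%).**

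| S | Pooled table | All stoppers, r = 0 | r = 1/3 | r = 1/2 |
|---|---|---|---|---|
| 5 | 28.6% | 28.6% | 33.3% | 35.7% |
| 15 | 22.2% | 22.2% | 33.3% | 38.9% |
| 30 | 16.7% | 16.7% | 33.3% | 41.7% |

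With separate denominators the table is too high at r = 0, right at r = 1/3 and too low at r = 1/2.

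**All three reasons (assumed).** Take 40 stops: 15 for improvement, 15 for inadequate response (IR) and 10 for adverse events (AE), one reason each. The shares of all stoppers are 37.5%, 37.5% and 25%.

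| Assumed switching (improved / IR / AE) | Kept in tally | Separate denominators | Pooled denominator (40) |
|---|---|---|---|
| 0% / 80% / 50% | 15, 3, 5 (of 23) | 65%, 13%, 22% | 37.5%, 7.5%, 12.5% |
| 0% / 40% / 25%, whole patients | 15, 9, 8 (of 32) | 47%, 28%, 25% | 37.5%, 22.5%, 20% |
| 40% / 40% / 40% | 9, 9, 6 (of 24) | 37.5%, 37.5%, 25% | 22.5%, 22.5%, 15% |

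The AE and IR counts fall in every row. The improvement share rises only with separate denominators and unequal switching. The one-reason simplification matters a little, because Table 3.2.2 counts every reason a patient gives.

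**The case against.** The rule can be defended as a disclosed, non-overlapping disposition. The table is titled for survey discontinuation, and those patients form its first tally, with their own reasons and a stated denominator. They are not missing from the table. That stands: what is absent is only the breakdown of these patients by reason for stopping Humira.

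A reader might infer that the table overstates improvement as a reason for stopping. The documents do not establish this. It needs separate denominators and less switching among improvers. After week 52 a patient can stop on improvement, remain under observation and start another biologic later. That patient is excluded too, which makes the improvement count too low.

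A reader might also infer that the safety and effectiveness picture as a whole is biased favourably. The documents do not support that either. Adverse events within the follow-up period remain in Tables 5.1, 5.1.1 and 5.2.1, including the week 52 to 108 onset category. Table 3.1 gives time to treatment completion, and Tables 5.8.1 and 5.8.2 give continuation curves for the whole safety set. No planned effectiveness estimate draws on Table 3.2.2.

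Finally, it cannot be said that the excluded patients are mainly switchers. The SAP list also has missed visits and other reasons, and no proportions are given. The third CRF itself is not in the documents, so how completely the stop reason is recorded for these patients is unknown.

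None of this answers the narrower point that the counts by reason are short and do not follow the SAP's own definition.

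**Conclusion.** The point holds for the counts. Table 3.2.2 under-reports adverse-event and inadequate-response stops after week 52 whenever at least one survey-discontinued patient stopped for that reason, and the shortfall equals the number of such patients. This needs no assumption about denominators. The table also departs from the discontinuer definition in SAP 10.1, and no other table in the SAP is specified to give these reasons.

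The distortion of percentages is conditional, and its size cannot be derived because the documents give no counts. The shares in the working are illustrations on assumed inputs.

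The consequence is confined to one descriptive output. The week-52 primary endpoint precedes the third-CRF period and is unaffected. It is still worth correcting: SAP 3.1 says the results may feed regulatory reporting and the reexamination application, and the plan already draws the stop reason from the third CRF.

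**What to change.** In Table 3.2.2:
- Replace the exclusion with a tabulation of the Humira stop reason, from the final third-CRF treatment record, for every third-CRF discontinuer as defined in SAP 10.1.
- Cross-classify that tabulation by survey discontinuation (yes or no), and use the undescribed category where no reason is recorded.
- Keep survey discontinuation as a separate tally that may overlap with the first.
- State that the denominator for stop reasons is all Humira discontinuers in the third CRF.

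The cost is a change of SAP wording and one extra tabulation from a field the plan already uses, with no new data collection. The two tallies would no longer add up to a mutually exclusive disposition, so a footnote should say so. The gain depends on how often the reason is filled in for patients whose survey ended, which the undescribed row will show.
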